13.2 Monitoring

The central and on-site monitoring requirements for this trial have been developed in conjunction with the trial specific risk assessment and are documented in the trial specific monitoring plan.

13.2.1 On-site monitoring

For this trial, all sites will be monitored in accordance with the trial risk assessment and monitoring plan. Any monitoring activities will be reported to the Trial Office and any issues noted will be followed up to resolution. Additional on-site monitoring visits may be triggered. PIs and site research teams will allow the OXYPuF trial staff access to source documents as requested. The monitoring will be conducted by BCTU/UoB staff.

13.2.2 Central monitoring

The Trial Office will check received ICFs and CRFs for compliance with the protocol, data consistency, missing data and timing at a frequency and intensity determined by the Data Management Plan. Sites will be sent DCFs requesting missing data or clarification of inconsistencies or discrepancies.

13.3 Audit and inspection

The Investigator will permit trial-related monitoring, audits, ethical review, and regulatory inspection(s) at their site and provide direct access to source data/documents. The investigator will comply with these visits and any required follow-up. Sites are also requested to notify the Trial Office of any relevant inspections or local audits.

13.4 Notification of Serious Breaches

In accordance with the Medicines for Human Use (Clinical Trials) Regulations 2004 and its amendments, the Sponsor of the trial is responsible for notifying the licensing authority in writing of any serious breach of the conditions and principles of GCP in connection with that trial or of the protocol relating to that trial, within 7 days of becoming aware of that breach. For the purposes of this regulation, a "serious breach" is a breach which is likely to affect:

- the safety or physical or mental integrity of the participants of the trial;
- the scientific value of the trial.

Sites are therefore requested to notify the Trial Office of any suspected trial-related serious breach of GCP and/or the trial protocol as soon as they become aware of them. Where the Trial Office is investigating whether or not a serious breach has occurred, sites are also requested to co-operate with the Trial Office in providing sufficient information to report the breach to the MHRA where required and in undertaking any corrective and/or preventive action

Sites may be suspended from further recruitment in the event of serious and persistent non-compliance with the protocol and/or GCP, and/or poor recruitment.

14. END OF TRIAL DEFINITION

The end of trial will be 6 months after the last data capture, including DCFs. This will allow sufficient time for the completion of protocol procedures, data collection and data input. The Trial Office will notify the REC and RGT within 90 days of the end of trial. Where the trial has terminated early, the Trials Office will inform the MHRA and REC within 15 days of the end of trial. The Trials Office will provide the REC and RGT with a summary of the clinical trial report within 12 months of the end of trial

15. STATISTICAL CONSIDERATIONS

15.1 Sample size

To detect an absolute minimum clinically important difference (MCID) of 4.0 points in the K-BILD Total score between groups, assuming a standard deviation of 8.85 as reported in the study which derived it (55), with 90% power and 5% significance level (2-sided type I error), a total of 104 participants per group will be needed to be randomised, 208 in total. Assuming and adjusting for approximately 20% dropouts, 260 participants will need to be recruited. The MCID of 4 being used here is slightly larger than the effect size in a crossover trial of AOT in fibrosis patients (mean difference K-BILD 3.7 (17)), however this tested HRQoL at 2 weeks, effects may grow with time, particularly if patients are more able to participate in activity or therapeutic interventions beneficial over 6 months, such as exercise training (56).

15.2 Analysis of outcomes

A separate Statistical Analysis Plan will be produced and will provide a more comprehensive description of the planned statistical analyses. A brief outline of the planned analyses is given below. The primary comparison groups will be composed of those randomised to AOT and standardised breathlessness advice versus those randomised to standardised breathless advice alone. In the first instance, all analyses will be based on the intention to treat principle, i.e. all participants will be analysed in the intervention group to which they were randomised irrespective of adherence to randomised intervention or protocol deviations. For all outcomes, appropriate summary statistics and differences between groups, e.g., mean differences will be presented, with 95% confidence intervals (95% CI) and p-values from two-sided tests also provided. Where possible, intervention effects will be adjusted for the minimisation variables listed in section 6.4.1, and also baseline K-BILD score. These variables will be treated as fixed effects, apart from centre which will be included as a random effect. No adjustment for multiple comparisons will be made. Statistical significance will be set to $p < 0.05$ (two sided) and all model estimates will be supported with 95% CI. All analysis will be done in STATA (version 14.0 or higher).

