2.2. Main trial objectives

2.2.1. Clinical aims and objectives

To determine whether AOT is clinically and cost effective in patients with idiopathic pulmonary fibrosis (IPF). The clinical objectives are determined as follows:

- Whether HRQoL measured using the K-BILD questionnaire is superior after AOT compared to the standardised breathlessness advice alone at 6 months after using the trial allocation.
- Whether breathlessness, determined by the MRC dyspnoea score, is superior after AOT compared to the standardised breathlessness advice alone at 6 months after using the trial allocation.
- Whether exercise capacity and physical activity, as measured by the 6MWT OR the sit to stand test (according to local protocol), and a self-reported activity questionnaire (IPAQ) respectively is superior after AOT compared to the standardised breathlessness advice alone at 6 months after using the trial allocation.

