8.2.2.1 Clinical

- Subscales within K-BILD (breathlessness, activity, chest symptoms)
- MRC Score
- Exercise capacity using the 6MWT or 1 minute sit to stand
- Physical activity using the IPAQ
- Sleepiness using the Epworth Sleepiness Scale
- Hospitalisations (all cause and IPF specific)
- Cough using a 6 point VAS
- Targeted adverse events
- Mortality (6 months, and from medical record only at 12 months)

- Medication use: benzodiazepines, antifibratics; ACEis and opiates for breathlessness.
- Completion of pulmonary rehabilitation
- Scheduled and unscheduled health service use relating to IPF.

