9. TRIAL PROCEDURES

The following should be performed/collected at baseline:

Clinic visit 1 (Baseline):

- Weight & Height
- Medical history
- Smoking status
- Shortness of breath (MRC dyspnoea score)
- Spirometry within the last 6 months
- Blood Gases (if saturations are <90% on air as per usual care)
- Full Blood Count (FBC/CBC) and storage of plasma for translational work
- Gas Transfer Test within the last 6 months
- Lung function tests
- Assessment of desaturation both on and off oxygen via either the 6MWT or 1 minute sit to stand
- Completion of the participant completed booklet

In addition, at the baseline visit, following randomisation, advice on breathlessness should be given to all participants, and for those randomised to the AOT arm, the oxygen prescription should be provided. For those centres taking part in the sub-study, interest by the participant in taking part in the sub-study should be ascertained.

The following should take place at the 3 week telephone follow up:

3 weeks post randomisation for AOT arm only:

- Telephone (3 weeks post randomisation) **Completed by staff at BCTU.**

- *The timescale as to when this telephone call takes place depends on when the participant receives the AOT. Depending on site/demand, this may take 2-3 weeks following referral to the oxygen team following randomisation.*

The following should be performed at 3 months follow up:

Clinic Visit 2 (3 months) *May be conducted via video depending on local policy*

- Review prescription for Study
- Survival Check
- SAE
- Completion of EQ-5D-L
- Healthcare utilisation
- SpO₂ check

The following should be performed/collected at 6 months follow up:

Clinic Visit 3 (6 months)

- Survival Check
- SAE Check
- Clinical review
- Check completion of HRQoL
- Blood Gases (if saturations are <90% on air as per usual care)
- Full Blood Count (FBC/CBC) and storage of plasma for translational work
- Recording of lung function (spirometry and gas transfer) if done as part of usual care
- Check completion of HRQoL
- Healthcare utilisation
- Weight
- Smoking status
- Shortness of breath (MRC dyspnoea score)
- Assessment of desaturation both on and off oxygen via either 6MWT or 1 minute sit to stand

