15.2.1 Primary outcome

The primary outcome K-BILD will be assessed based on whether AOT is superior to usual care, and will follow an intention to treat analysis.

K-BILD recording over 6 months, will be analysed using mixed effects GEE to calculate an adjusted mean difference between groups, and corresponding 95% CI. The p-value relating to the intervention group parameter as generated by the model will be presented

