15.2.2 Secondary outcomes

Patient characteristics will be summarised using mean and standard deviation (SD) for continuous data.

Continuous secondary outcomes (e.g., K-BILD subscales, VAS for cough) will be analysed as per the primary outcome.

Categorical outcomes (e.g, Hospitalisations, Adverse events, Mortality) will be presented as frequency counts and percentages. Frequency of hospitalisations and adverse events will be analysed using Poisson regression techniques. Binary outcomes (Scheduled/Unscheduled health services use, Completion of pulmonary rehabilitation, Progress to LTOT) will be analysed using log-binomial regression model to calculate the adjusted relative risk and 95% confidence interval. Mortality data, will be analysed using Cox proportional hazard techniques given the assumptions of proportionality are met, and an adjusted hazards ratio with a 95% confidence interval will be presented.

Regarding safety, the total number of patients experiencing SAEs will be given by intervention group along with a descriptive table of the events, and statistical significance will be determined by a chi-square test.

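### Section 15.2 names baseline K-BILD as the only baseline score for adjustment, so continuous secondary outcomes, read literally, are not adjusted for their own baselines, and precision is lost

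*Protocol*

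**What the plan says.** Section 15.2 (Analysis of outcomes) presents itself as a short outline: "A separate Statistical Analysis Plan will be produced and will provide a more comprehensive description of the planned statistical analyses". The same paragraph is general in scope: "For all outcomes, appropriate summary statistics and differences between groups, e.g., mean differences will be presented". Its covariate rule is: "Where possible, intervention effects will be adjusted for the minimisation variables listed in section 6.4.1, and also baseline K-BILD score". No other baseline score is named there or elsewhere in section 15.

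The primary K-BILD outcome "will be analysed using mixed effects GEE to calculate an adjusted mean difference between groups" (15.2.1). Section 15.2.2 adds: "Continuous secondary outcomes (e.g., K-BILD subscales, VAS for cough) will be analysed as per the primary outcome".

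Table 2 (Schedule of assessments) lists K-BILD, MRC, cough VAS, IPAQ and the 6MWT on and off oxygen at both baseline and 6 months. The visit list in section 9 allows the 1 minute sit-to-stand in place of the walk.

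Section 8.2.2.1 lists as a single outcome "Exercise capacity using the 6MWT or 1 minute sit to stand", and section 2.2.1 leaves the choice of test to local protocol. At 6 months section 9 asks for "Assessment of desaturation both on and off oxygen via either 6MWT or 1 minute sit to stand". No section says which of the two runs supplies the exercise-capacity outcome.

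**The concern.** Baseline K-BILD is the right covariate for 6-month K-BILD because it is that outcome's own starting value. For cough, self-reported activity or walking distance, a total quality-of-life score would normally predict the 6-month value less well than the participant's own earlier measurement of the same thing. An analyst who follows 15.2 to the letter would put the weaker predictor in the model and leave out the stronger one, although it has already been collected.

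Breathlessness, exercise capacity and physical activity are named clinical objectives (2.2.1). For these, the confidence intervals would be wider than the data require, and any chance imbalance in the outcome's own baseline would stay in the estimate.

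Exercise capacity raises a further question. One test gives metres and the other repetitions. The only stated rule for continuous secondary outcomes leads to one adjusted mean difference, and nothing says how the two tests are to be handled within it.

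**Working it through.** **The plan's own figure.** The sample size uses a difference of 4.0, SD 8.85, 90% power and two-sided 5% (15.1). The normal approximation is n = 2(1.960 + 1.282)² × 8.85² / 4.0² ≈ 102.9, so 103 per group; the exact two-sample t-test gives 104. Then 2 × 104 = 208, and 208 / 0.80 = 260. All three stated figures are reproduced. They concern the K-BILD total, which is adjusted for its own baseline, so this point does not touch them.

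**Effect of the covariate choice.** If a covariate has correlation r with the outcome (after the minimisation variables, which are in the model either way), adjustment leaves a residual variance of (1 − r²)σ². Write r_K for the correlation with baseline K-BILD and r_own for the correlation with the outcome's own baseline. Then

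SE ratio = √[(1 − r_K²) / (1 − r_own²)].

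The protocol gives neither correlation, so all values below are assumptions. With r_own = 0.7, 1 − r_own² = 0.51.

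| r_K | Variance ratio | SE ratio | Share of sample effectively lost |
|---|---|---|---|
| 0.2 | 0.96 / 0.51 = 1.88 | 1.37 | 1 − 1/1.88 = 47% |
| 0.3 | 0.91 / 0.51 = 1.78 | 1.34 | 1 − 1/1.78 = 44% |
| 0.4 | 0.84 / 0.51 = 1.65 | 1.28 | 1 − 1/1.65 = 39% |

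In the middle row, 208 analysed participants are worth about 208 × 0.51 / 0.91 ≈ 117 in an own-baseline analysis. Power for an effect of 0.3 SD with 104 per group is 62% with K-BILD adjustment and 86% with own-baseline adjustment.

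**Wider assumptions (SE ratio).**

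| | r_own 0.5 | r_own 0.7 | r_own 0.8 |
|---|---|---|---|
| r_K 0.1 | 1.15 | 1.39 | 1.66 |
| r_K 0.3 | 1.10 | 1.34 | 1.59 |
| r_K 0.5 | 1.00 | 1.21 | 1.44 |

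**K-BILD subscales.** The baseline total contains the subscale items, so r_K should be close to r_own. With r_own = 0.7 and r_K of 0.6 to 0.7 (assumed), the SE ratio is √(0.64 / 0.51) = 1.12 falling to √(0.51 / 0.51) = 1.00.

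**Exercise capacity, only if pooled in raw units.** Assume an effect of 30 m on the walk (SD 100) and 1.8 repetitions on sit-to-stand (SD 6), which is 0.3 SD on each test. The pooled mean difference is then 30p + 1.8(1 − p), where p is the share of participants who walk. That is 8.85, 15.9 and 22.95 for p = 0.25, 0.50 and 0.75. The same effect in SD units gives a different figure, in no unit, according to the mix of sites.

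**The case against.** The strongest reply is that 15.2 is a declared outline and that covariates for each secondary outcome are normal content for the SAP, which is not shown. The rule is also softened by its opening qualifier and does not forbid further covariates. Analysing an outcome in the same way as the primary can fairly be read as adjusting each outcome for its own baseline, as K-BILD is for K-BILD. A repeated-measures reading of 15.2.1, with baseline as one of the responses, would also bring the own baseline in.

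Much of this stands as a limit on the point, but it does not remove it. The protocol does more than leave the covariate open: it names one, in a paragraph about all outcomes. The favourable readings have to be supplied by the reader.

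Several stronger readings are tempting and are not supported:

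- *Every secondary outcome is affected.* The SAE comparison is an unadjusted chi-square test. Mortality, hospitalisation and completion of rehabilitation have no comparable baseline value. The subscales lose little.
- *The plan pools metres with repetitions, so the exercise result is uninterpretable.* No section says the tests are pooled, and none says they are kept apart. Exercise capacity is not among the examples of continuous outcomes in 15.2.2.
- *On-oxygen results in the AOT arm will be set against off-oxygen results in controls.* Section 9 asks for both conditions without restriction by arm, so a like-for-like comparison is available. The remark in 1.2.1 that acute gains fade concerns COPD studies and does not settle the matter here.
- *The estimates would be biased.* Under randomisation, omitting a prognostic baseline costs precision only.

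One limit applies to the remedy. The Epworth scale is a secondary outcome but is not named in Table 2 or in the section 9 baseline list, so a baseline value cannot be assumed for it.

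**Conclusion.** The point holds in a limited form. As written, 15.2 and 15.2.2 lead to adjustment for baseline K-BILD alone among baseline scores. For cough VAS, IPAQ, exercise capacity and (if modelled) MRC, a better covariate is already collected and is not named.

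The consequence is lost precision: standard errors 28% to 37% too large under the central assumptions (r_own 0.7, r_K 0.2 to 0.4), and anywhere from 0% to 66% too large across the wider grid. These sizes rest wholly on assumed correlations. The direction does not, provided an outcome's own baseline predicts it better than baseline K-BILD does.

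The handling of the two exercise tests and of the oxygen condition is unspecified rather than wrong, and calls for clarification only. The primary analysis and the sample size of 260 are unaffected.

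**What to change.** Replace the covariate sentence in 15.2 with wording such as: *Each continuous or ordinal secondary outcome that has a baseline measurement will be adjusted for its own baseline value and the minimisation variables; the K-BILD total will be adjusted for baseline K-BILD total and the minimisation variables.* For Epworth, either confirm in the schedule that a baseline is taken or state that only the minimisation variables are used.

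As a secondary clarification, add that 6MWT distance and sit-to-stand repetitions will be analysed separately, or combined only as within-test standardised scores. State also which oxygen condition supplies the exercise outcome, and that arms are compared under that same condition.

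The cost is two or three sentences. No new data are needed for the outcomes in Table 2. The drawback is that separate exercise analyses each use only the participants at sites running that test, while a standardised combination keeps the numbers but reports the effect in SD units.

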15.2.1 Primary outcome

The primary outcome K-BILD will be assessed based on whether AOT is superior to usual care, and will follow an intention to treat analysis.

K-BILD recording over 6 months, will be analysed using mixed effects GEE to calculate an adjusted mean difference between groups, and corresponding 95% CI. The p-value relating to the intervention group parameter as generated by the model will be presented

15.2.2 Secondary outcomes

Patient characteristics will be summarised using mean and standard deviation (SD) for continuous data.

Continuous secondary outcomes (e.g., K-BILD subscales, VAS for cough) will be analysed as per the primary outcome.

Categorical outcomes (e.g, Hospitalisations, Adverse events, Mortality) will be presented as frequency counts and percentages. Frequency of hospitalisations and adverse events will be analysed using Poisson regression techniques. Binary outcomes (Scheduled/Unscheduled health services use, Completion of pulmonary rehabilitation, Progress to LTOT) will be analysed using log-binomial regression model to calculate the adjusted relative risk and 95% confidence interval. Mortality data, will be analysed using Cox proportional hazard techniques given the assumptions of proportionality are met, and an adjusted hazards ratio with a 95% confidence interval will be presented.

Regarding safety, the total number of patients experiencing SAEs will be given by intervention group along with a descriptive table of the events, and statistical significance will be determined by a chi-square test.

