4. ELIGIBILITY

4.1. Inclusion criteria

- Aged 18 or over
- Clinically diagnosed IPF, confirmed by an ILD multi-disciplinary team (MDT) linked to an NHS specialist commissioned IPF service
- Breathlessness with MRC dyspnoea score ≥2
- Willing and able to comply with completion of questionnaires out to 6 months post-randomisation
- Able to complete a 6MWT or 1 minute sit to stand test
- Able to use oxygen safely in the opinion of the local investigator

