7.7. Intervention supply and storage

7.7.1. Intervention supplies

Local HOSAR (home O2 assessment and review services) will provide oxygen according to normal NHS practice to those patients randomised to the AOT group.

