16.2 Data Collection

Health care resource use information will be collected on IPF-related primary care visits, visits to other health care professionals, prescribed medications, LTOT and hospital admissions (A&E, length and nature of inpatient admissions) using a healthcare utilisation CRF at 3 and 6 months. Information on wider costs of informal care and productivity losses will also be collected. The cost of AOT and the breathlessness advice time will be determined within the trial, as will other interventions such as antifibrotics and pulmonary rehabilitation. Unit costs from standard UK sources, for example NHS Reference costs will be sought for all health care resource use items. In order to calculate QALYs, the EQ-5D-5L questionnaire will be administered to patients at baseline, 3 and 6 months. The crosswalk value set will be applied to patient responses to obtain utility scores, in line with current NICE recommendations.

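### Analysing scheduled/unscheduled health-service use as yes/no makes scheduled use insensitive to changes in the number of contacts; it should be analysed as two counts.

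*Protocol*

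**What the plan says.** Protocol section 8.2.2.1 lists among the clinical secondary outcomes "Scheduled and unscheduled health service use relating to IPF". Section 15.2.2 fixes its scale and model: "Binary outcomes (Scheduled/Unscheduled health services use, Completion of pulmonary rehabilitation, Progress to LTOT) will be analysed using log-binomial regression model", giving an adjusted relative risk with a 95% confidence interval. The same section models the frequency of hospitalisations by Poisson regression.

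Four other places bear on the point:

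- **Population (4.1).** The IPF diagnosis must be "confirmed by an ILD multi-disciplinary team (MDT) linked to an NHS specialist commissioned IPF service".
- **Supply of the intervention (7.7.1 and 9).** The home oxygen assessment and review service "will provide oxygen according to normal NHS practice to those patients randomised to the AOT group". Section 9 says of the time to receive AOT that "this may take 2-3 weeks following referral to the oxygen team following randomisation".
- **Data collected (16.2).** Resource use covers "IPF-related primary care visits, visits to other health care professionals, prescribed medications, LTOT and hospital admissions", recorded "using a healthcare utilisation CRF at 3 and 6 months".
- **Economic analysis (16.3).** Mean resource use is calculated for each category of care and reported in a cost-consequence analysis.

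The protocol does not say whether scheduled and unscheduled use form one indicator or two, or which contacts count. It gives no expected proportion or rate.

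**The concern.** The natural reading of a binary service-use outcome is any use against none. Patients followed by a specialist IPF service will mostly have at least one scheduled IPF-related contact in 6 months, whichever arm they are in. A treatment that lowers or raises the number of contacts moves few patients between none and some, so the relative risk stays close to 1 while the rate changes. If the slash in section 15.2.2 means one merged indicator, scheduled use would also swamp unscheduled use.

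There is a second difficulty. By design only AOT patients are supplied through the oxygen service after randomisation. If those contacts count and controls are somewhat below 100%, the comparison may show an excess in the AOT arm that reflects only delivery of the intervention.

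At stake is the reading of one named secondary outcome: a real change in contacts could be reported as no difference, or supply of oxygen could be reported as an effect on service use.

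**Working it through.** **The plan's own figure.** The only design calculation is for K-BILD (section 15.1): difference 4.0, SD 8.85, two-sided 5%, 90% power. The standard two-means formula gives 103 per group, against 104 stated, which agrees. Then 208 / 0.8 = 260. I use 104 analysed per arm below.

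**Assumptions (none of these is in the protocol).** The binary outcome is any against none. The control mean is m = 2, 3 or 4 scheduled contacts in 6 months. AOT truly reduces the rate by 25%, so the AOT mean is 0.75m. Counts are Poisson, or negative binomial with k = 2.

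**Formulas.**

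- P(any) = 1 − exp(−m) for Poisson; 1 − (k/(k+m))^k for negative binomial.
- Largest possible relative risk = 1 / P(any in controls).
- Yes/no power: two-proportion z-test, two-sided 5%.
- Count power: Φ(|ln 0.75| / SE − 1.96), with SE² = [(1/m + 1/k) + (1/(0.75m) + 1/k)] / 104. The 1/k terms are zero for Poisson.

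Example, Poisson with m = 3: P(any) = 1 − e^−3 = 95.0% in controls and 1 − e^−2.25 = 89.5% under AOT, so RR = 0.94 and yes/no power is 32%. For counts, SE = √[(0.3333 + 0.4444)/104] = 0.0865, 0.2877/0.0865 = 3.33, and power is 91%.

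| Model | m | Any use, control | Any use, AOT | RR | RR cap | Power, yes/no | Power, count |
|---|---|---|---|---|---|---|---|
| Poisson | 2 | 86.5% | 77.7% | 0.90 | 1.16 | 38% | 78% |
| Poisson | 3 | 95.0% | 89.5% | 0.94 | 1.05 | 32% | 91% |
| Poisson | 4 | 98.2% | 95.0% | 0.97 | 1.02 | 24% | 97% |
| Neg. bin., k = 2 | 2 | 75.0% | 67.3% | 0.90 | 1.33 | 23% | 51% |
| Neg. bin., k = 2 | 3 | 84.0% | 77.8% | 0.93 | 1.19 | 20% | 59% |
| Neg. bin., k = 2 | 4 | 88.9% | 84.0% | 0.94 | 1.12 | 18% | 64% |

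A 20% reduction gives the same ordering. For Poisson, power is 21% against 75% at m = 3 and 11% against 92% at m = 5.

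**Oxygen-service contacts.** Suppose they count and bring the AOT arm to about 100%. With controls at 80% or 90%, power to declare a difference is 99.9% or 92%, with supply alone as the cause. With controls at 95%, 98% or 99%, power is 64%, 30% or 17%.

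**Unscheduled use on its own.** At assumed control proportions of 30%, 50% and 70%, power for a relative risk of 0.7 is 32%, 59% and 88%. There is no ceiling here.

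**The case against.** A reader might infer that the whole outcome sits at its ceiling and cannot show an effect. The documents do not support that, for three reasons.

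- Every reason for a high proportion concerns scheduled use. Nothing in the protocol puts unscheduled IPF-related use near 100%.
- With overdispersed counts, any use is only 75–89% and the relative risk could reach 1.12–1.33.
- A high proportion does not by itself remove power. At 98% in controls, a true relative risk of 0.9 for any use has 80% power. The loss arises because a change in the number of contacts produces a much smaller change in any against none.

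A reader might also infer that the 3- and 6-month trial visits force scheduled use to 100%. No section says that trial visits count as service use.

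It can fairly be added that section 15.2 calls itself a brief outline, so counting rules may belong in the SAP. Section 16.2 does not name home-oxygen review among its resource-use items and treats the cost of AOT separately. Volume of use is analysed in section 16.3, and hospitalisation frequency is modelled by Poisson regression in section 15.2.2, so the information is not lost to the trial. In a pragmatic intention-to-treat trial, oxygen-service contacts are real NHS use caused by allocation, and simply removing them could favour AOT.

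Most of this stands and limits the point. It does not remove it. The binary scale and the model are stated in the protocol, not left open, and they concern a listed clinical outcome for which quantities are needed anyway.

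**Conclusion.** The concern holds for scheduled use, and for a merged indicator if that is what is meant. Scored yes/no, this outcome is insensitive to changes in the number of contacts. Under the assumptions above, power for a 25% reduction is 24–38% (Poisson) or 18–23% (k = 2) as yes/no, against 78–97% or 51–64% as counts. The count analysis does better in every case examined. If oxygen-service contacts are included, a difference that reflects only supply of AOT is also possible; whether it appears depends on a control proportion that the protocol does not give.

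The sizes rest entirely on assumed contact rates, dispersion and effect. The direction rests on patients being under specialist follow-up and on the any-against-none reading. The trial was sized for K-BILD alone, so low power for a secondary outcome is not in itself an error. The point is that a better analysis of the same data is available at almost no cost. The primary analysis and the sample size are unaffected.

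**What to change.** In section 15.2.2, take scheduled/unscheduled service use out of the binary list. Analyse the number of scheduled contacts and the number of unscheduled contacts over 6 months as two separate counts, with an overdispersion-robust rate model: negative binomial, or Poisson with robust standard errors. Use the quantities already needed for costing under sections 16.2 and 16.3.

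State that protocol-mandated trial visits are not counted. Report oxygen assessment, supply and review contacts as a separate line, and show the scheduled-contact comparison both with and without them. This keeps the pragmatic comparison visible while separating delivery of AOT from other use.

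The cost is a change of wording and slightly more analysis work.
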